5.2. Exclusion Criteria

Participants are excluded from the study if any of the following criteria apply:

Medical Conditions:

1. Participants with any other active malignancy within 3 years prior to enrollment, except for adequately treated basal cell or squamous cell skin cancer, or carcinoma in situ of the cervix, Bowen's disease. Participants with other stable indolent malignancies and no evidence of progressive disease may be considered after discussion with sponsor.
2. Participants sustaining major surgery defined as a complex procedure performed under regional or general anesthesia or conscious sedation with a recovery period of at least 4 weeks prior to study intervention.
3. Participants with primary immunodeficiency.

4. Participants who require immunosuppressive therapy including, but not limited to, treatment with corticosteroids in pharmacologic doses (equivalent to ≥ 10 mg prednisone daily).
 - Topical, ocular, intra-articular, intranasal or inhalational corticosteroids with minimal systemic absorption are permitted.
 - Short course (≤ 7 days) of corticosteroids prescribed prophylactically (eg, contrast drug allergy) or for the treatment of nonautoimmune conditions (eg, hypersensitivity reaction) are permitted.
5. Participants with active autoimmune conditions or history of autoimmune diseases that may relapse with the following exceptions:
 - Controlled Type 1 diabetes mellitus;
 - Hypothyroidism (managed with hormone replacement);
 - Controlled celiac disease;
 - Skin diseases not requiring systemic therapy (eg, vitiligo, psoriasis, alopecia).
6. History of interstitial lung disease, pneumonitis (non-infectious) or uncontrolled lung diseases.
7. History of allogeneic transplant.
8. History of prior irAEs Grade ≥ 3 .
9. Participants with central nervous system metastases; however participants who have undergone surgery and/or radiation for brain metastases who are asymptomatic and radiologically stable and are no longer taking corticosteroids. Participants with leptomeningeal metastases are not eligible.
10. Active inflammatory GI disease, known diverticular disease or previous lap-band surgery. Impairment of GI function or GI disease that may significantly alter the absorption of PF-07265028, such as history of GI surgery with may result in intestinal blind loops and participants with clinically significant gastroparesis, short bowel syndrome, unresolved nausea, vomiting, active inflammatory bowel disease or diarrhea of NCI CTCAE Grade > 1 . Proton-pump inhibitors are not allowed at least 7 days prior to C1D1 and throughout the study.
11. Hypertension that cannot be controlled by medications ($> 150/90$ mm Hg despite optimal medical therapy).

12. Any of the following in the previous 6 months: myocardial infarction, congenital long QT syndrome, Torsades de pointes, arrhythmias (including sustained ventricular tachyarrhythmia and ventricular fibrillation), right bundle branch block and left anterior hemiblock (bifascicular block), unstable angina, coronary/peripheral artery bypass graft, symptomatic congestive heart failure (New York Heart Association class III or IV), cerebrovascular accident, transient ischemic attack, or symptomatic pulmonary embolism; DVT; arterial occlusive disease; ongoing cardiac dysrhythmias of NCI CTCAE Grade ≥ 2 , atrial fibrillation of any grade that is uncontrolled, or QTcF interval >470 ms at screening.
13. Known or suspected hypersensitivity to active ingredient/excipients of study treatments.
14. Other medical or psychiatric condition including recent (within the past year) or active suicidal ideation/behavior or laboratory abnormality that may increase the risk of study participation or, in the investigator's judgment, make the participant inappropriate for the study .

Exceptions:

- Limited, focal radiation therapy (including Gamma-Knife) require only a 3-day period before study entry and the absence of any radiation-induced complications.
- Palliative radiation therapy within 14 days of study entry (2 weeks in the case of immunotherapy) and the absence of any radiation-induced complications.

Prior/Concomitant Therapy:

15. Prior administration of HPK1 inhibitor.
16. Prior systemic anti-cancer therapy within 14 days (6 weeks for mitomycin C or nitrosoureas) prior to study treatment. Participant with prostate cancer are permitted to continue on LHRH agonists/antagonists.
17. Concomitant use or anticipated need for food (eg grapefruit juice), supplements (eg, St John's Wort), or drugs (eg, ketoconazole) that are known strong and/or moderate CYP3A4 inhibitors, or strong CYP3A4 inducers, including their administration within 10 days or 5 half-lives of the CYP3A4 inhibitor/inducer (whichever is longer) prior to the first dose of study intervention. Please see [Section 10.8](#) for a comprehensive drug list.
18. Concomitant or anticipate use of sensitive substrates with NTI for CYP3A4, CYP2D6, UGT1A1, P-gp, and highly sensitive substrates for BCRP. Please see [Section 10.8](#) for a comprehensive drug list.
19. Receipt of a live vaccine within 30 days of enrollment.

20. Current use of any prohibited concomitant medication(s) or those unwilling/unable to use a permitted concomitant medication(s). Refer to [Section 6.8 Concomitant Therapy](#).
21. Transfusion of RBCs or platelets or administration of hematopoietic growth factors within 2 weeks of C1D1.

Prior/Concurrent Clinical Study Experience:

22. Participation in other studies involving investigational drug(s) within 4 weeks or 5 half-lives (whichever is shorter) prior to planned first dose. Cases must be discussed with sponsor's medical monitor to judge eligibility.

Diagnostic Assessments:

23. Serum or urine pregnancy test (for WOCBP) positive at screening.
24. While SARS-CoV2 testing is not mandated for entry into this protocol, testing should follow local clinical practice standards. If a participant has a positive test result for SARS-CoV2 infection, is known to have asymptomatic infection, or is suspected of having SARS-CoV2, he/she is excluded. See [Section 10.10](#) for more information around SARS-CoV2
25. HBV, HCV, known HIV- or AIDS related illness. This protocol excludes participants with active infections but permits inclusion of participants who meet the following conditions:
 - Human immunodeficiency virus (HIV) infected participants must be on a protocol permitted antiretroviral therapy (ART) (See Appendix 10.8 for prohibited concomitant medications) and have a well-controlled HIV infection/disease defined as:
 - a CD4+ T cell count >350 cells/mm³ at time of screening;
 - must have achieved and maintained virologic suppression defined as confirmed HIV RNA level below 50 copies/mL or the lower limit of qualification (below the limit of detection) using the locally available assay at the time of screening and for at least 12 weeks prior to screening;
 - must have been on a stable regimen of ART, without changes in drugs or dose modification, for at least 4 weeks prior to study entry (Cycle 1 Day 1);
 - HIV screening tests are not required unless there is known history of HCV infection or as mandated by local health authority.

Participants who are hepatitis B surface antigen positive are eligible if they have received hepatitis B virus (HBV) antiviral therapy for at least 4 weeks and have undetectable HBV viral load prior to enrollment. Note: Participants should remain on antiviral therapy throughout study intervention and follow local guidelines for HBV antiviral therapy post completion of study intervention. Hepatitis B screening tests are not required unless there known history of HBV infection or as mandated by local health authority.

Participants with a history of hepatitis C virus (HCV) infection are eligible if HCV viral load is undetectable at screening. Note: Participants must have completed curative antiviral therapy at least 4 weeks prior to enrollment. Hepatitis C screening tests are not required unless there is a known history of HCV infection or as mandated by local health authority.

Japan only: Participant who are tested viral load positive for HBV at any time during the study will interrupt administration of PF-07265028 and should consider starting treatment immediately in parallel with consultation with hepatologist per local practice.

Other Exclusions:

26. Investigator site staff or Pfizer employees directly involved in the conduct of the study, site staff otherwise supervised by the investigator, and their respective family members.

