5. STUDY POPULATION

This study can fulfill its objectives only if appropriate participants are enrolled. The following eligibility criteria are designed to select participants for whom participation in the study is considered appropriate. All relevant medical and nonmedical conditions should be taken into consideration when deciding whether a particular participant is suitable for this protocol.

Prospective approval of protocol deviations to recruitment and enrollment criteria, also known as protocol waivers or exemptions, is not permitted.

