6.8.9. Surgery

Caution is advised for any surgical procedures during the study. The appropriate interval of time between surgery and PF-07265028 required to minimize the risk of impaired wound healing and bleeding has not been determined. Stopping PF-07265028 is recommended at least 7 days prior to surgery. Postoperatively, the decision to reinitiate PF-07265028 treatment should be based on a clinical assessment of satisfactory wound healing and recovery from surgery.

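### Exclusion criterion 2 on major surgery gives no recent-surgery washout on either grammatical reading, and both readings conflict with other criteria in Protocol 5.2

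*Protocol*

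**What the plan says.** The lead-in to Protocol 5.2 sets the direction of the list: "Participants are excluded from the study if any of the following criteria apply". Criterion 2 begins "Participants sustaining major surgery defined as a complex procedure performed under regional or general" and continues "anesthesia or conscious sedation with a recovery period of at least 4 weeks prior to study intervention".

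Other timed exclusions in the same section state a look-back window, for example criterion 19, "Receipt of a live vaccine within 30 days of enrollment", and criterion 21, "Transfusion of RBCs or platelets or administration of hematopoietic growth factors within 2 weeks of C1D1".

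Section 5 adds: "Prospective approval of protocol deviations to recruitment and enrollment criteria, also known as protocol waivers or exemptions, is not permitted". Section 8 repeats that waivers are not allowed.

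The only other text on the interval between surgery and the drug is 6.8.9, which deals with operations during the study. It says: "The appropriate interval of time between surgery and PF-07265028 required to minimize the risk of impaired wound healing and bleeding has not been determined". The synopsis list of selected exclusions has no major-surgery item.

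**The concern.** In an exclusion list, a criterion that is met keeps the participant out. Criterion 2 contains no word such as *within*, *less than* or *without* that would turn the 4-week phrase into a minimum recovery requirement. A site applying it literally gets a result that the rest of 5.2 does not support, and two sites can get different results.

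Two things are at stake.

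- **Safety at entry.** This is a first-in-human study, and 6.8.9 concedes that the safe interval for wound healing and bleeding is unknown. Criterion 2 is the only general pre-entry surgical criterion that contains a time element.
- **Who is enrolled.** Followed literally, the criterion turns away participants who have recovered from earlier major surgery. Section 8.2.1 records previous surgery for the cancer as routine history, so such candidates are expected at screening.

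There is also a possible route to the Part 1 primary endpoint. Under 4.3.3, a Cycle 1 event that meets the DLT definition counts unless it is plainly explained by the disease or a concurrent illness. Surgical complications are not named there.

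**Working it through.** No plan figure is involved, so the check is logical: apply the criterion as written to a few cases, then look for text that corrects the result.

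**The two readings**

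- *Reading A, time condition.* The words about study intervention follow directly on the 4-week phrase, so it reads as the interval between the operation and dosing. Criterion 2 is met when that interval is 4 weeks or more.
- *Reading B, definition.* The 4-week recovery describes the kind of operation that counts as major. Criterion 2 is met by any such operation before study intervention, with no look-back limit.

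| Case | A | B | An ordinary washout |
|---|---|---|---|
| Major surgery 10 days before first dose | not excluded by criterion 2 | excluded | excluded |
| Major surgery, 4 weeks or more of recovery | excluded | excluded | not excluded |
| Major surgery years earlier | excluded | excluded | not excluded |

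The B column assumes that the operation is of a kind needing at least 4 weeks of recovery. A gives the opposite of a washout in all three rows. B agrees with a washout in the first row only.

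**Against the neighbouring criteria**

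- *Criterion 9* makes an exception for participants operated on for brain metastases who are asymptomatic, stable and off corticosteroids; the synopsis version states outright that they may enter. A bars those with 4 or more weeks of recovery. B bars all whose operation meets the definition.
- *Criterion 12* limits the bypass-graft exclusion to the previous 6 months. A participant with an older graft passes criterion 12, but fails criterion 2 under A, and under B if the operation meets the definition. The 6-month limit then does almost nothing.
- *Criterion 10* singles out lap-band surgery and GI surgery that could affect absorption. That selection is largely redundant if older major surgery already excludes.

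**Search for correcting text**

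- Synopsis exclusions: no surgery item.
- 6.8.9: on-study surgery only, and the interval is stated to be undetermined.
- Inclusion 13: requires acute effects of prior therapy to have resolved, with an exception left to the investigator; it sets no time since surgery.
- Exclusion 14: general risk and investigator judgment, with no surgical interval.
- SAP: nothing on eligibility after surgery.

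No passage supplies a pre-entry surgery window.

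**The case against.** The strongest reply has four parts.

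1. *The intent is obvious from context.* Criteria 9, 10 and 12 and the surgical history collected under 8.2.1 show that recovered surgical patients are expected, so most sites would guess the meaning. This is probably true. But the same context shows that neither literal reading is right, and an operative eligibility rule should not depend on guessing.
2. *Recently operated participants may be kept out anyway.* Reading B excludes them. Under reading A, exclusion 14, inclusion 13 and, for transfused participants, exclusion 21 would stop some. Section 6.3.1 also requires the sponsor's written confirmation of enrolment before dosing. This stands in part: these are backstops, but none sets a recovery time.
3. *The waiver ban does not prevent clarification.* This is correct. The sponsor can clarify the criterion for all sites; what is barred is an exemption for an individual.
4. *The route to the DLT endpoint is speculative.* It needs a recently operated enrollee, a qualifying complication in Cycle 1, and a judgment that the attribution exception does not apply. SAP 6.1.1 leaves the final call to the dose level review meeting, and Protocol 10.11.3 allows equivocal events a weight of 0.5. This stands, and no effect on dose escalation is claimed here.

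**Conclusion.** Criterion 2 is defective as written. It either excludes recovered participants and misses recently operated ones, or excludes any qualifying surgery at any time. Both outcomes conflict with criteria 9, 10 and 12, and nothing elsewhere repairs them. The conclusion rests on the wording of 5.2 alone and holds whichever reading is taken.

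Three stronger conclusions are tempting, and the documents do not support them.

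- A reader might infer that the criterion is simply reversed. That is reading A only; reading B is grammatically open.
- A reader might infer that the protocol admits people operated on days before dosing. Even under A, criterion 2 merely fails to exclude them, and other criteria may still do so.
- A reader might infer a measurable loss of candidates or a shift in the escalation. The documents give no share with prior major surgery and define the Part 2 population by tumor type and checkpoint-inhibitor resistance, not by previous resection. No count can be derived.

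The defect applies to every part of the study. It should be corrected, but it touches no estimand or planned analysis directly.

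**What to change.** Reword criterion 2 so that it has two separate elements: what counts as major surgery (type of procedure and anesthesia), and the time condition, with insufficient recovery as the ground for exclusion. One possible form: *Major surgery, as defined by procedure and anesthesia type, from which the participant has not completed the required recovery time (4 weeks, if confirmed) before first study intervention.* The 4 weeks is the protocol's own figure; the sponsor should confirm that it is the intended minimum. Whether it is clinically right is not judged here.

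Reconcile the new wording with criteria 9, 10 and 12, so that a participant acceptable under those items is not barred by criterion 2 without intent. Add the item to the synopsis exclusions.

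The cost is one sentence and one synopsis line in a protocol amendment. Some recently operated candidates may have to wait longer before dosing.

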5.3. Lifestyle Considerations

5.3.1. Contraception

The investigator or his or her designee, in consultation with the participant, will confirm that the participant has selected an appropriate method of contraception for the individual participant and his or her partner(s) from the permitted list of contraception methods (see [Appendix 4 10.4.4](#)) and will confirm that the participant has been instructed in its consistent and correct use. At time points indicated in the [schedule of activities \(SoA Table 1\)](#), the investigator or designee will inform the participant of the need to use highly effective contraception consistently and correctly and document the conversation and the participant's affirmation in the participant's chart (participants need to affirm their consistent and correct use of at least 1 of the selected methods of contraception) considering that their risk for pregnancy may have changed since the last visit. In addition, the investigator or designee will instruct the participant to call immediately if the selected contraception method is discontinued or if pregnancy is known or suspected in the participant or partner.

5.3.2. Photosensitivity

Participants will be advised to report any reaction to sun exposed skin. If a photosensitivity reaction occurs in a participant, special precautions should then be taken to limit any potential photo irritation effect, by minimizing the participants' exposure to light including sunlight, and exposure to high intensity UVA and UVB light sources such as tanning beds, tanning booths and sunlamps. Furthermore, for photosensitive participants, these individuals should be encouraged to apply sunscreen/sunblock daily and to wear clothing that covers areas of exposed skin when outdoors during daylight hours.

5.4. Screen Failures

Screen failures are defined as participants who consent to participate in the clinical study but are not subsequently enrolled in the study. A minimal set of screen failure information is required to ensure transparent reporting of screen failure participants to meet the CONSORT publishing requirements and to respond to queries from regulatory authorities. Minimal information includes demography, screen failure details, eligibility criteria, and any SAE.

Individuals who do not meet the criteria for participation in this study (screen failure) may be rescreened, up to a limit of 1 time. Rescreened participants should be assigned a new participant number.

6. STUDY INTERVENTIONS AND CONCOMITANT THERAPY

Study intervention is defined as any investigational intervention(s), marketed product(s), placebo, medical device(s), or study procedure(s) intended to be administered to a study participant according to the study protocol.

For the purposes of this protocol, study intervention refers to PF-07265028 and sasanlimab.

6.1. Study Interventions Administered

On days when study intervention is administered in clinic, PF-07265028 is administered first and then followed by sasanlimab.

Study Interventions		
Intervention Name	PF-07265028	Sasanlimab Solution for Injection, 50 mg/mL
ARM Name (group of participants receiving a specific treatment (or no treatment))	All	Combination therapy (Parts 1B and Part 2A)
Type	Drug	Biologic
Dose Formulation	Tablet	Vial
Unit Dose Strength(s)	5 mg, 25 mg, or 100 mg tablet	50 mg/mL, 2 mL vial
Dosage Level(s)	Dose amount and frequency – reference the study scheme/figure or text below as appropriate	300 mg Q4W
Route of Administration	Oral	SC
Use	Experimental	Experimental
IMP or NIMP	IMP	IMP
Sourcing	Provided centrally by the sponsor See IP manual and/or IRT Guide for ordering the intervention	Provided centrally by the sponsor See IP manual and/or IRT Guide for ordering the intervention
Packaging and Labeling	Study intervention will be provided in a 30-count HPD bottle. Each bottle will be open-labeled as required per country requirement.	Study intervention will be provided in a 2 mL vial. Each vial will be open-labeled as required per country requirement.
Current/Former Names or Aliases	PF-07265028, HPK1	Sasanlimab, PF-06801591, or PD-1 inhibitor

6.1.1. Administration

6.1.1.1. PF-07265028

Participants will swallow PF-07265028 tablets whole with at least 8 ounces (240 mL) of water, and will not manipulate or chew the study intervention prior to swallowing. PF-07265028 will initially be administered QD by mouth for all cohorts on a continuous basis. Participants who are unable to swallow whole tablets may dissolve their dose in oral syringe(s) as outlined in the IP manual to allow for suspension administration either orally or via an NG tube. If supported by emerging data, BID continuous regimen may be considered. A cycle is defined as 28 days, regardless of missed doses or dose delays.

Participants will take PF-07265028 at approximately the same time within each dosing interval (ie, ± 3 hours of nominal time). On site visit days, participants will take the drug at the site after performing predose assessment. On other days, participants will be instructed to self-administer the drug at home. A dosing diary will be given to each participant to support at home dosing. The participants will be requested to note the date and time of each dose, food consumption status at the time of drug administration.

If a participant misses a dose at the scheduled time, the participant can still take the dose within 4 hours of the scheduled time. If the participant missed taking a dose after 4 hours of the scheduled time, or day of treatment, they must be instructed not to “make it up” but resume subsequent doses as prescribed. This dose will be considered as a missed dose. In addition, if a participant vomits any time after taking a dose, they should not “make it up” but to resume subsequent doses as prescribed. Lastly, if a participant inadvertently takes 1 extra dose during a day, the participant should not take the next dose of PF-07265028.

Food Requirements (Except for the Food-Effect Subset or Cohorts Evaluating Food Intake on Tolerability)

Participants will take PF-07265028 orally with at least 8 oz (240 mL) of water on an empty stomach. No food or liquids other than water will be consumed for 2 hours before and 2 hour following each dose throughout the study).

These empty stomach requirements may be removed (via a letter to the investigators) if results from the food-effect subset indicate there is no clinically meaningful effect of food on the PK of PF-07265028. If food is demonstrated to improve tolerability for participants included in the cohorts where PF-07265028 is administered with food, participants in all cohorts may be instructed to take PF-07265028 with a meal.

Food Requirements for the Food-Effect Subset

Participants enrolled in the food-effect subset will take PF-07265028 under the fasted and fed conditions on Cycle 1 Day 15 and Day 16, respectively, and under empty stomach condition for the remaining portion of the study.

Fasted condition: Following an overnight fast of at least 6 hours, PF-07265028 will be administered and continue fasting for an additional 2 hours postdose. Water will be allowed ad libitum except for 1 hour before and 1 hour after drug administration.

Fed condition: Following an overnight fast of at least 6 hours, participants will start a high-fat/high-calorie breakfast in the clinical sites within 30 minutes prior to and finish breakfast before administration of PF-07265028. No additional food will be allowed until at least 2 hours postdose. Water will be allowed ad libitum except for 1 hour before and 1 hour after drug administration. The breakfast will be high-fat (approximately 50% of total caloric content of the meal) high-calorie (approximately 800-1000 calories with 150, 250, and 500-600 calories from protein, carbohydrate, and fat, respectively) meal.

Food Requirements for Cohorts Evaluating the Effect of Food on PF-07265028 Tolerability

Each dose of PF-07265028 will be administered with a meal and with approximately 8 ounces (240 mL) of water.

